3.1 Primary Objective

The primary objective of this study is to quantify the psychological, social and emotional impact of comprehensive aesthetic treatment with a portfolio of Allergan products by measuring the change in subject's satisfaction with facial appearance from baseline (before any treatment) to the final study visit (██████████ FACE-Q™: Satisfaction with Facial Appearance). These Allergan products include BOTOX Cosmetic, BELKYRA, Juvéderm HA facial fillers, and SkinMedica® topical nonprescription skin care products, as described in Section 9.

3.2 Secondary Objectives

Secondary objectives are:

- To determine the subject's self-appraisal of expectations of life change (██████████ FACE-Q™: Expectations), age-related facial appearance (██████████ FACE-Q®: Aging Appraisal), psychological function (██████████ FACE-Q™: Psychological Function), social function (██████████ FACE-Q™: Social Function) and overall satisfaction with skin (██████████ FACE-Q™ Satisfaction with Skin Questionnaire).
- To quantify the investigator's and subject's assessment of aesthetic improvement.

4 Study Design

4.1 Study Design Overview

This Phase 4 study is a prospective, interventional, multicenter, combination medical device, drug, and skin care postmarketing study. Each subject will be in the study for up to 11 months depending on the treatments given, and act as his/her own control. All products will be used as per their license only. The investigators will perform all treatments and evaluations.

[figure not shown]
The study is planned to enroll 60 subjects consecutively at approximately 6 study sites in Canada. The ratio of subjects treated with BELKYRA to subjects without BELKYRA treatment will be approximately 1:2 (ie, approximately 20 BELKYRA subjects and 40 subjects without BELKYRA) based on clinical indication and the decision of the subject and investigator. Thus approximately one-third of all subjects will receive BELKYRA treatment. Recruitment will also target men, who are typically under-represented in aesthetic studies.

Detailed descriptions of all study procedures by study visit and study treatment are presented in Table 6.1 and Section 6.

All subjects will sign an informed consent form (ICF) and begin at the screening visit (V0). Subjects receiving BELKYRA treatment will enter the study at V1 continuing on to V12. There will be at least 1 month between repeat BELKYRA treatments and the final BELKYRA treatment.

Subjects not receiving BELKYRA following screening (V0) will enter the study at V7 to begin treatment with Juvéderm HA facial fillers, SkinMedica, and BOTOX Cosmetic, as indicated in the study design diagram (Figure 4.1).

Figure 4.1 Overall Study Design

4.2 Study Endpoints

4.2.1 Primary Endpoint

The primary endpoint is the change from before any treatment (screening, V0) in the Rasch-transformed score of the FACE-Q Satisfaction with Facial Appearance Overall Scale to the final study visit (V12).

4.2.2 Key Secondary Endpoints

4.2.2.1 FACE-Q Questionnaires

- Subject's assessment of expectations of life change as measured by the mean change from baseline before any treatment in the Rasch-transformed score of the FACE-Q Expectations scale to final study visit (V12)
- Subject's assessment of age-related facial appearance as measured by the mean change from screening before any treatment in the Rasch-transformed score of the FACE-Q Aging Appraisal to final study visit (V12)
- Subject's assessment of psychological well-being as measured by the mean change from screening before any treatment in the Rasch-transformed score the FACE-Q Psychological Function Scale to final study visit (V12)
- Subject's assessment of social function as measured by the mean change from baseline before any treatment in the Rasch-transformed score of the FACE-Q Social Function scale to final study visit (V12)

- Subject's assessment of overall satisfaction with skin as measured by the mean change from screening before any treatment in the Rasch-transformed score of the FACE-Q Satisfaction with Skin to final study visit (V12)

4.2.2.2 Self-Perception of Age Questionnaire

Subject's assessment of age-related facial appearance by the self-perception of age (SPA) measure at baseline before any treatment to final study visit (V12); responders are defined as having achieved a younger category.

[figure not shown]
4.2.3 Other Secondary Endpoints

4.2.3.1 Global Aesthetic Improvement Scale

- Change in investigator's assessment of global facial aesthetic improvement as measured by the 5-point global aesthetic improvement scale (GAIS) at final study visit (V12)
- Change in subject's assessment of global facial aesthetic improvement as measured by the 5-point GAIS at final study visit (V12)

4.2.3.2 Periorbital Aesthetic Appearance Questionnaire

- Change in subject's satisfaction with appearance of periorbital area as measured by the periorbital aesthetic appearance questionnaire (PAAQ)

4.3 Safety

All adverse events (AEs) including injection site reactions (ISRs) will be collected from when the ICF is signed through to the last study visit (V12). Serious adverse events (SAEs) will be reported within the specified time and format directly to Allergan and SkinMedica as described in Section 10.8.1.

4.4 Blinding and Randomization

Blinding and randomization are not applicable. This is an open-label, single-arm study. Subjects are enrolled consecutively into study groups based upon subject need. Investigators will perform all treatments and evaluations.

5 Selection of Subjects

Approximately 60 subjects will be enrolled at approximately 7 sites in Canada. Subjects will be assigned to study treatment only if they meet all of the inclusion criteria and none of the exclusion criteria. Subjects who discontinue treatment will not be replaced.

5.1 Inclusion Criteria

The following are requirements for entry into the study.

[figure not shown]
Applies to BELKYRA Subjects Only

1. Clinical report of Grade 2 or 3 on the submental fat rating scale (SMFRS; [REDACTED]).
2. Subject report of dissatisfaction with submental area; rating of 0, 1, or 2 using the subject self-rating scale (SSRS; [REDACTED]).

Applies to All Subjects

1. 30 to 65 years of age, inclusive, at screening (male or female)
2. Accept the obligation not to receive any other facial procedures or treatments at any time during the study that are not related to the study
3. Women of childbearing potential must have a negative urine pregnancy test before each injectable treatment and practice a reliable method of contraception throughout the study

5. Willing to avoid direct and prolonged sun exposure to the facial skin, which includes tanning beds, for the duration of the study

5.2 Exclusion Criteria

The following criteria exclude potential subjects from participating in the study:

Applies to BELKYRA Subjects Only

1. History of any intervention to treat SMF (eg, liposuction, surgery, or lipolytic agents)
2. History of trauma associated with the chin or neck areas that in the judgment of the investigator may affect evaluation of safety or efficacy of treatment
3. An anatomical feature (eg, predominant subplatysmal fat, loose skin in the neck or chin area, prominent platysmal bands) for which reduction in SMF may, in the judgment of the investigator, result in an aesthetically unacceptable outcome

4. Evidence of any cause of enlargement in the submental area (eg, thyroid enlargement, cervical adenopathy, ptotic submandibular gland) other than localized SMF
5. Any medical condition (eg, respiratory, cardiovascular, hepatic, neurological disease, or thyroid dysfunction) that would interfere with assessment of safety or efficacy or compromise the subject's ability to undergo study procedures or give informed consent

Applies to All Subjects

[figure not shown]
2. Body mass index (BMI) > 30
3. Known allergy or sensitivity to the study products or their components
4. Pregnant, lactating, or planning to become pregnant at any time during the study
5. Received BOTOX Cosmetic or treatment with any other botulinum toxin product for any condition within 6 months before enrollment
6. Received (or is planning to receive) anticoagulation, antiplatelet or thrombolytic medications (eg, warfarin) or other substances known to increase coagulation time from 10 days prior to injection and up to 3 days post-injection
7. Undergone plastic surgery of the face and/or neck, tissue grafting, or tissue augmentation with silicone, fat, or other permanent dermal fillers, or be planning to undergo any of these procedures at any time during the study
8. Has undergone temporary or semi-permanent facial or neck dermal filler treatment (e.g., hyaluronic acid, calcium hydroxylapatite, poly-L-lactic acid) within 12 months before enrollment
9. Received mesotherapy, skin resurfacing (laser, photomodulation, intense pulsed light, radio frequency, dermabrasion, chemical peel, or non-ablative procedures) in the face or neck within 6 months prior to study enrollment

11. Lip tattoos, facial hair or scars that would interfere with visualization of the lips and perioral area for the effectiveness assessments
12. At any proposed injection site, presence of inflammation, infection at any injection site or systemic infection (study entry may be postponed until one week following recovery), noticeable acne scarring, cancerous or pre-cancerous lesion, or unhealed wound or have undergone radiation treatment in the area to be treated
13. Received any investigational product within 60 days prior to study enrollment or planning to participate in another investigation during the course of this study
14. An employee (or a relative of an employee) of the investigators, Allergan, or representative of Allergan
15. Condition or in a situation that, in the investigator's opinion, may put the subject at significant risk, may confound the study results, or may interfere significantly with the subject's participation in the study
16. Current use of oral corticosteroids
17. Current use of nonsteroidal anti-inflammatory drugs (NSAIDs) (eg, aspirin, ibuprofen), from 10 days prior to injection up to 3 days post-injection
18. Prescription topical retinoid therapy and/or topical hormone cream applied to the face, for potential subjects who have not been on a consistent dose regimen for at least 6 months prior to enrollment and who are unable to maintain regimen for the study
19. Systemic retinoid therapy within one year prior to study enrollment

21. Medical condition that may increase the risk of exposure to botulinum toxin including diagnosed myasthenia gravis, Eaton-Lambert Syndrome, amyotrophic lateral sclerosis, or any other disease that might interfere with neuromuscular function
22. Current use of aminoglycoside antibiotics, curare-like agents, or agents that might interfere with neuromuscular (skeletal) function
23. Profound atrophy/excessive weakness of muscles in target areas of injection
24. History of facial nerve palsy
25. Anticipated need for treatment with botulinum toxin of any serotype for any reason during the study (other than study treatment)
26. Very thin skin in the mid-facial region
27. Tendency to accumulate fluid in the lower eyelids, or large infraorbital fat pads, ie, significant convexity or projection from the infraorbital fat pads
28. Mid-face volume deficit due to congenital defect, trauma, abnormalities in adipose tissue related to immune-mediated diseases such as generalized lipodystrophy (eg, juvenile dermatomyositis), partial lipodystrophy (eg, Barraquer-Simons syndrome), inherited disease, or human immunodeficiency virus–related disease
29. Undergone oral surgery or other dental procedures (eg, tooth extraction, orthodontia, or implantation) within 30 days prior to enrollment or be planning to undergo any of these procedures during the study
30. Subjects with neuromuscular disorders including generalized muscle weakness, diplopia, ptosis, dysphonia, dysarthria, severe dysphagia, and respiratory compromise
31. Subjects with a history of allergies or hypersensitivity to HA or lidocaine

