5.3 Summary of Required Washout Periods

Potential study subjects may have used the following products and procedures (Table 5.2) that have specified washout periods prior to baseline visits for all subjects.

6 Study Plan and Procedures

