7.3 Concomitant Medications

Therapy considered necessary for the subject's welfare may be given at the discretion of the investigator, including but not limited to medications for other conditions (ie, hypertension, diabetes, etc.), treatment of AEs, estrogens, androgens, anti-androgenic agents, vitamins, iron supplements, folate, and herbal supplements. Medications should be taken consistently throughout the study and at the investigator's discretion.

Concomitant medications as defined for this study include dietary supplements, over-the-counter medications, and oral herbal preparations, as well as changes in dosages of current prescription medications. Concomitant medications will be documented for each subject at each scheduled visit. A detailed history of medications will be documented at screening. Subsequently, at each study visit, subjects will be asked what medication, if any, they have taken since the previous visit. All concomitant medications will be recorded on electronic case report forms (eCRFs).

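### Exclusion 18, as printed, joins its two topical retinoid/hormone-cream conditions with 'and', so it does not screen out recent starters who will continue or long-stable users who cannot continue

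*Protocol*

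**What the plan says.** Item 18 of the all-subject exclusions in Protocol section 5.2 runs in two parts. The first sets the scope and opens the first condition: "Prescription topical retinoid therapy and/or topical hormone cream applied to the face, for potential subjects who have not been on a". The second completes that condition and adds another: "consistent dose regimen for at least 6 months prior to enrollment and who are unable to maintain regimen for the study". The synopsis carries the same wording, so neither place corrects the other.

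The neighbouring text that bears on it:

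- Item 19 covers a different route: "Systemic retinoid therapy within one year prior to study enrollment".
- Item 15 lets the investigator exclude a subject whose condition or situation "may confound the study results".
- Section 5.3 refers to a table of "specified washout periods prior to baseline visits for all subjects". The content of that table (Table 5.2) is not in the readable text.
- Section 7.3 gives a general instruction: "Medications should be taken consistently throughout the study".
- Section 4.4 states the design: "This is an open-label, single-arm study". Section 4.1 adds that each subject serves as their own control.
- Section 4.2.2.1 lists the endpoint closest to a topical skin drug among the key secondary endpoints: "Subject's assessment of overall satisfaction with skin as measured by the mean change from screening before any treatment". FACE-Q Aging Appraisal is in the same list.
- SAP section 8.4 tabulates and lists concomitant medications. The readable SAP plans no adjustment or sensitivity analysis for them.

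**The concern.** The evident purpose of item 18 is stable topical exposure from well before baseline to V12. That purpose fails if either condition is met: the regimen is recent, or it will not last. Joined by 'and', the criterion acts only when both are met. The six-month requirement then has no force for anyone who can continue, and the requirement to continue has no force for anyone already stable for six months.

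The design gives this weight. With no concurrent group, a skin effect from a prescription topical that starts working, or wears off, between V0 and V12 cannot be separated from the effect of study treatment. Non-prescription skin care products are themselves part of that treatment, so the two effects overlap. SAP section 10.3 applies the primary endpoint's methods, including the test against zero, to the skin and aging scales. With concomitant medication only tabulated, eligibility is the main safeguard.

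**Working it through.** **1. The logic of item 18.** For users of a facial prescription retinoid or hormone cream, let A = regimen not consistent for at least 6 months, and B = unable to maintain it. The printed rule excludes if A and B. Stable exposure requires excluding if A or B.

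| User | A | B | Printed 'and' | With 'or' |
|---|---|---|---|---|
| Recent start, cannot continue | yes | yes | excluded | excluded |
| Recent start, will continue | yes | no | passes | excluded |
| Long-stable, cannot continue | no | yes | passes | excluded |
| Long-stable, will continue | no | no | passes | passes |

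The printed rule excludes 1 of 4 combinations and 'or' excludes 3 of 4. The two middle rows are the gap.

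**2. Drafting elsewhere in the list.** Items 6, 7, 13 and 29 each pair something past with something planned, and each uses 'or'. Item 18 departs from that pattern.

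**3. Whether another readable rule closes the gap.**

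- Inclusion 2 bars unrelated facial treatments during the study. Item 18 implies that a stable topical may continue, so inclusion 2 is hard to read as banning one already in use. It does nothing about stopping.
- Item 19 is limited to systemic retinoids.
- Section 6.2.5.1 names surgery and cosmetic procedures.
- Section 7.3 is an instruction, not an eligibility rule. For a recent starter it would keep the confounder running.
- Item 15 could be used, but depends on opinion at each site.
- Table 5.2 and all-subject items 1, 10 and 20 cannot be read, so they cannot be checked.

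**4. Scale of a possible bias.** The plan gives no figure, so this part is illustrative. If a share q of subjects is affected and the topical moves their score by b points, the mean change shifts by q × b. Both q and b are assumptions. Protocol section 11.6 supplies the reference values: planned mean change 12.0, SD 20.0, 48 evaluable subjects, two-sided 5% test. (The 90% power stated there for 48 subjects does not reproduce: 32 suffice, and 48 give 98.3%. That is a separate matter and does not affect this point.) The last column is the probability of rejecting when the true change is zero, from the noncentral t distribution with noncentrality (shift/20) × √48.

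| q | b | Shift | Shift / 12.0 | Rejection probability |
|---|---|---|---|---|
| 5% (3 of 60) | 5 | 0.25 | 2% | 0.051 |
| 10% (6 of 60) | 10 | 1.0 | 8% | 0.063 |
| 15% (9 of 60) | 20 | 3.0 | 25% | 0.175 |
| 30% (18 of 60) | 20 | 6.0 | 50% | 0.530 |

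These rows treat every affected subject as a recent starter whose score improves. Stoppers with a negative b would offset part of the shift. The documents give no planned change or SD for the skin and aging scales, so the same comparison cannot be made there.

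**The case against.** The best defence is that item 18 is ambiguous rather than wrong. Because the pronoun is repeated before the second condition, ordinary English allows it to name two groups, both excluded, and a site that grasps the purpose may apply it that way. That is fair, and it means admission of such subjects is not demonstrated. It does not remove the need to settle the wording: an eligibility rule that sites can read in two ways will be applied unevenly.

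Second, the readable text is incomplete. A washout entry in Table 5.2 might catch some recent starters, and the unreadable items might bear on the point. This limits the claim to what item 18 itself does. A washout before baseline would still not catch a subject who stops later.

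Third, the medication history at screening and the records of dose changes at each visit (section 7.3) should make affected subjects identifiable. That stands and helps repair, although the SAP makes no use of it beyond tables and listings.

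A reader might also infer that in both cases the topical drug's effect is credited to study treatment. The documents do not support that. It fits the recent starter, if the drug improves the skin. Benefit lost by a stopper may instead count against study treatment.

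**Conclusion.** As printed, item 18 leaves two kinds of unstable topical user eligible under that item, and no readable mandatory criterion catches them. Their change scores would be confounded, most directly on FACE-Q Satisfaction with Skin and Aging Appraisal and less so on the primary scale. A recent starter likely inflates the change; for a stopper the sign is uncertain.

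The conclusion rests on the literal reading of 'and' and on nothing in the unseen table or items closing the gap. Neither the number affected nor the bias can be derived from the documents. On the assumed middle case the primary mean change shifts by 1.0 point, which is modest; the largest illustrated effect needs 30% affected and 20 points each. It would go too far to infer that the primary result is unreliable on this account. The limits on attribution that come from an uncontrolled, open-label design would also remain after the wording is corrected.

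**What to change.** In Protocol section 5.2, item 18, and in the matching synopsis item, replace the 'and' that introduces the second condition with 'or', so that failing either condition excludes. If inability is meant to include a subject who intends to stop, the item should say so. Check the amended item against Table 5.2 so that the two do not conflict.

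If enrolment has already begun, use the medication records to flag subjects in the two middle rows of the table above and repeat the skin-related analyses without them.

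The cost is one short amendment and a few more screen failures among current topical users. The sample size calculation is unaffected.

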5.3 Summary of Required Washout Periods

Potential study subjects may have used the following products and procedures (Table 5.2) that have specified washout periods prior to baseline visits for all subjects.

6 Study Plan and Procedures

6.1 Study Subject Number

[figure not shown]
Subjects who meet all inclusion/exclusion criteria will be assigned a subject enrollment number via the electronic data system that will serve as the subject identification number on all study documents.

[figure not shown]
6.2 Description of Study Days

[figure not shown]
Study procedures, treatments, and assessments will be performed at the study visits as listed below and as shown in Table 6.1.

[figure not shown]

[figure not shown]
Table 6.1 Schedule of Study Procedures, Treatments, and Assessments

[figure not shown]

[figure not shown]

6.2.4 Unscheduled/Missed Visits

Each time the subject returns to the study site, the investigator (or designee) will solicit and record information about ISRs, other AEs, and concomitant medications. An interim or unscheduled visit may replace a scheduled visit if it occurs within the acceptable time window for a scheduled visit or if the scheduled visit was missed. All applicable procedures should be performed.

6.2.5 Restrictions and Precautions

6.2.5.1 Prohibited Medications and/or Treatments

Subjects must not undergo any type of facial plastic or reconstructive surgery or cosmetic procedure (eg, plastic surgery; tissue grafting; tissue augmentation with silicone, fat, or other permanent, semi-permanent, or temporary dermal fillers; neuromodulator injections; or mesotherapy; or ablative procedures) at any time during this study.

The decision to administer a prohibited medication/treatment will be made with the safety of the study participant as the primary consideration. When possible, Allergan or Allergan's

representative should be notified before a prohibited medication/treatment is administered. Prior to attending study visits, subjects must not apply facial cosmetics.

6.2.5.2 Special Diet or Activities

Within the first 24 hours after filler treatment, on V7, and if a touch-up treatment is performed on V8 and V9, subjects should avoid strenuous exercise, extensive sun or heat exposure, and alcoholic beverages. Exposure to any of the above may cause temporary redness, swelling, and/or itching at the injection sites.

7 Methods of Assessment and Endpoints

